**Appendix 2 Schedule of Assessments - Module 2**

	Module 2 (RXC004 + Nivolumab) Schedule of Assessments										
	Pre-Screening	Screening	Cycle 0 (3-7 days)	Cycle 1 (28 day cycle)		Cycle X Day 1 (28 day cycles)	IP Discontinuation	30 day Safety Follow-up 	90 day Safety Follow-up 	PFS Follow-up	
Window	n/a	-28 to -1	D1	D1	D15 +/- 1d	+/- 3d	Within 7 days of discontinuation	+/- 3d	+/- 3d		
Pre-Screening informed consent (optional)	X										
Diagnostic / Archival tumour tissue (optional)	X										
Genetic screening for RNF43/RSPO aberrations (optional)	X										
Informed consent		X									
Pharmacogenetics (optional consent and blood sample) 		X									
Demography & baseline characteristics		X									
Smoking status & alcohol consumption		X									
Medical/surgical history		X									
Inclusion/exclusion criteria**		X									
Bone Scan		X	As clinically indicated								

Module 2 (RXC004 + Nivolumab) Schedule of Assessments										
	Pre-Screening	Screening	Cycle 0 (3-7 days)	Cycle 1 (28 day cycle)		Cycle X Day 1 (28 day cycles)	IP Discontinuation	30 day Safety Follow-up l	90 day Safety Follow-up l	PFS Follow-up
Window	n/a	-28 to -1	D1	D1	D15 +/- 1d	+/- 3d	Within 7 days of discontinuation	+/- 3d	+/- 3d	
HepB, HepC and HIV testing		X								
Physical examination a		X	X	X		X	X			
ECOG/WHO performance status		X	X	X		X	X			
Pregnancy test (WOCBP only)		(X)	(X)	(X)		(X)				
Vital signs (including height and weight) b		X	X	X	X	X	X	X		
Clinical chemistry / Haematology		X	X	X	X	X	X	X	X	
TSH (reflex T3/T4) m		X		X	X	X	X	X	X	
Urinalysis*		X	X	X	X	X				
ECG		X	X	X	X	X h	X			
DXA scan (including VFA*** at baseline)		X				Cycle 2, 4 and 7, and every third cycle thereafter				
Tumour biopsy (optional - archive or newly acquired)		X			X g	X g				
Blood samples for bone turnover biomarkers		X			X	X	X			
Blood sample for circulating soluble factors c			X		X	X				

Module 2 (RXC004 + Nivolumab) Schedule of Assessments											
	Pre-Screening	Screening	Cycle 0 (3-7 days)	Cycle 1 (28 day cycle)		Cycle X Day 1 (28 day cycles)	IP Discontinuation	30 day Safety Follow-up l	90 day Safety Follow-up l	PFS Follow-up	
Window	n/a	-28 to -1	D1	D1	D15 +/- 1d	+/- 3d	Within 7 days of discontinuation	+/- 3d	+/- 3d		
Blood sample for PBMC (viable cells) c			X		X	X					
Fresh blood for PD analysis d			X		X	Cycle 2 Day 1 only					
Blood sample ctDNA analysis e			X		X	X	X				
Blood sample ctRNA analysis e			X n		X n	X n	X n				
RECIST 1.1 assessments (by CT/MRI) j		X	Every 8 weeks +/- 1 week from Cycle 1 Day 1 until RECIST1.1 defined disease progression								
Vitamin D3 and Calcium supplements		Patients should commence 800 IU vitamin D3 (Cholecalciferol) QD and 1000-1500 mg calcium QD supplements from ICF signature until RXC004 discontinuation									
Denosumab dosing o		120 mg sc Denosumab once every month from C0D1 until RXC004 discontinuation									
RXC004 dosing			X	Multiple dosing at cohort specified schedule							
Nivolumab dosing k				X		X					
RXC004 PK f			X	X	X	X	X				
Concomitant medication		X	X	X	X	X	X	X	X		
Adverse events		X	X	X	X	X	X	X	X		
Patient diary card review				X	X	X	X				

Module 2 (RXC004 + Nivolumab) Schedule of Assessments										
	Pre-Screening	Screening	Cycle 0 (3-7 days)	Cycle 1 (28 day cycle)		Cycle X Day 1 (28 day cycles)	IP Discontinuation	30 day Safety Follow-up 	90 day Safety Follow-up 	PFS Follow-up
Window	n/a	-28 to -1	D1	D1	D15 +/- 1d	+/- 3d	Within 7 days of discontinuation	+/- 3d	+/- 3d	
Subsequent anti-cancer therapy							X	X	X	X

**Footnotes - General**

Assessments made on Day 1 of each cycle are to be conducted prior to RXC004 administration, unless specified otherwise.

Additional assessments may be conducted as clinically indicated.

A tolerance of +/-1 day will be permitted for all study visits and a tolerance of -1 day for all assessments relative to the study visit, unless specified otherwise.

\* Female patients, if fertile, will require a serum pregnancy test at Screening and urine pregnancy on Day 1 of each cycle

\*\*Eligibility criteria to be re-checked at Cycle 1 prior to dose administration.

\*\*\*A lateral T & L spine assessment if a Vertebral Fracture Assessment (VFA) cannot be completed locally

- a A full physical examination is required at Screening and prior to Day 1 of each cycle ; Symptom-directed physical examination is acceptable at other time-points
- b Vital signs (heart rate, BP, temperature and respiration rate) will be assessed pre-dose and up to 1 hour after the RXC004 administration. Patient status will be monitored during RXC004 administration and repeat vital signs will be taken if needed. Height is required at screening only. Weight will be recorded at Screening and on Day 1 of each cycle.
- c Pre-first dose on Cycle 0 Day 1 and 4-6hrs post dose on Cycle 1 Day 15 and Day 1 of each subsequent cycle
- d Fresh blood samples to be collected from selected sites only (in close proximity to RedX laboratory). All samples should be collected pre-dosing.
- e Pre-first dose on Cycle 0 Day 1 and 4-6hrs post dose on Day 1 of each subsequent cycle and at progression/discontinuation
- f Patients will have PK blood sampling conducted at the following sample times  
 Cycle 0: Day 1 - Predose, then 30 mins, 1 h, 2 h, 4 h, 6 h, 8 h, 10 h, 12 h, 24 h, and 48 h post-dose.  
 Cycle 1, Day 15: Predose, then 30 mins, 1 h, 2 h, 4 h, 6 h, 8 h, 10 h, 12 h & 24 h  
 Cycle X, Day 1 - A single pre-dose sample will also be taken on subsequent samples on Day 1.  
 The SRC may advise on adjusted time-points. The actual time for each blood draw must be accurately recorded.
- g An optional 'on treatment' biopsy at C1D15 and during Cycle 3 of treatment, preferably from the same site as the baseline biopsy sample
- h On Cycle 0, Day 1 and Cycle 1, Day 1 a resting 12-lead ECG will be conducted pre-dose and 30 mins (+/- 15 mins) after RXC004 administration. On Day 1 of all other cycles, a resting 12-lead ECG will be conducted pre-dose only.
- i Consenting patients will have a 10 mL blood sample taken for preparation of a germ-line DNA sample at Screening (recommended time-point only).
- j CT (preferred) or MRI, each preferably with IV contrast. It is strongly recommended to maintain use of the same imaging modality (CT or MRI), acquisition protocol, facility and scanner across all imaging time points per patient. Note that where there is a rationale for assessment of bone lesions that develop after study start, these assessments will be performed as part of the CT or MRI assessment and will not require additional radiological bone scan assessment. Additional scans may be performed to confirm a Complete Response (CR) or Partial Response (PR) or disease progression (PD) as per appropriate response assessment guidelines. Any requirement for confirmatory scans will typically be performed at the next protocolled assessment time point. Other assessments e.g. whole body MRI or PET, are not protocol mandated, but may be performed as clinically indicated and at request of Investigator.
- k 480mg IV infusion over 60 minutes, q4w +/- 3 days, unless an infusion needs to held due to an adverse event. Results for chemistry, haematology and thyroid function labs must be available before commencing an infusion (within 3 days) and reviewed by the treating physician or Investigator prior to dosing. If a patient continues in the study on nivolumab alone, this treatment may be continued for a maximum of 12 months in total.
- l Follow up assessments should be performed 30 days after discontinuation of IP and 90 days after last dose of nivolumab
- m T3 and T4 will only be measured if TSH is abnormal or if there is clinical suspicion of an AE related to the endocrine system
- n For patients with Wnt ligand dependent tumours only (RNF43/RSPO aberrations or biliary/thymus cancers).

- o All patients must receive denosumab before first dose of RXC004. 120 mg sc denosumab should be administered approximately once every month from C0D1 until RXC004 discontinuation. Investigators may delay subsequent denosumab doses until the next scheduled visit providing that there is no significant increase in  $\beta$ -CTX compared to baseline, according to Investigator judgement

### Appendix 3 Performance Status Scale

ECOG	
Score	Description
0	Normal activity. Fully active, able to carry on all pre-disease performance without restriction.
1	Symptoms, but ambulatory. Restricted in physically strenuous activity, but ambulatory and able to carry out work of a light or sedentary nature (e.g., light housework, office work).
2	In bed <50% of the time. Ambulatory and capable of all self-care, but unable to carry out any work activities. Up and about more than 50% of waking hours.
3	In bed >50% of the time. Capable of only limited self-care, confined to bed or chair more than 50% of waking hours.
4	100% bedridden. Completely disabled. Cannot carry on any self-care. Totally confined to bed or chair.
5	Dead.

## Appendix 4 Response Evaluation Criteria for Solid Tumours (RECIST)

Term	Definition
Complete response (CR)	Disappearance of all target lesions. Any pathological lymph nodes must have reduction in short axis to <10 mm.
Partial response (PR)	A $\geq$ 30% decrease in the sum of diameters of target lesions, taking as reference the baseline sum diameters.
Progressive disease (PD)	At least a 20% increase in the sum of diameters of target lesions, taking as reference the smallest sum on study (this includes the baseline sum if that is the smallest on study). In addition to the relative increase of 20%, the sum must also demonstrate an absolute increase of at least 0.5 cm. The appearance of one or more new lesions is also considered progression.
Stable disease (SD)	Neither sufficient shrinkage to qualify for PR nor sufficient increase to qualify for PD, taking as reference the smallest sum diameters while on study.
New measureable lesions 	Always represents progressive disease (PD)
New nonmeasureable lesions	Always represents progressive disease (PD)
Non-index lesions	Changes contribute to defining best overall response of CR, PR, SD, and PD

From RECIST v1.1

- 1) Measureable lesion must be accurately measured in at least one dimension (longest diameter in the plane of measurement is to be recorded) with a minimum size of 10 mm by CT scan (CT slice thickness no greater than 5 mm)

## Appendix 5 Colitis Management and Treatment Guidelines

Events of colitis or enteritis were reported in four patients who commenced treatment at doses of 3 mg QD or 10 mg QD. Events of ileitis and colitis were subsequently reported in the ongoing Phase 2 studies (RXC004/0002 and RXC004/0003), at doses of 2mg QD, so there is a potential risk for colitis in patients receiving RXC004 2mg QD as a monotherapy.

RXC004-related diarrhoea/colitis may present as abdominal pain with other symptoms including intermittent constipation, diarrhoea, nausea and/or vomiting. In some cases, symptoms may be minimal. Blood and mucus in the stool may not be apparent.

Symptoms may be preceded by or accompanied by a raised CRP and neutrophil count.

If lower GI tract inflammation is suspected, infectious and other causes should be excluded, including CMV and *C .difficile*. Attempts should be made to definitively diagnose the condition with a CT scan, and colonoscopy/sigmoidoscopy with biopsy, if clinically safe to do so.

Nivolumab is known to cause colitis (See Appendix 8) so patients receiving the combination of RXC004 and nivolumab may be at higher risk of this event. These guidelines are consistent with guidance for nivolumab-related colitis. However, for patients who are receiving RXC004 plus nivolumab, please also refer to the most current version of the nivolumab SPC/USPI.

### Management:

Monitoring of CRP or fecal calprotectin levels may help to monitor the response to treatment.

Grade	Management
Grade 1 colitis (asymptomatic but evidence on CT scan)	Continue RXC004 at a lower dose and repeat the CT scan within 4 weeks. No action is needed for nivolumab.  No additional treatment is indicated. If the Grade 1 colitis is evident on the second scan despite the lower dose of RXC004, it should be managed as Grade 2 colitis and the scan should be repeated within 4 weeks

Grade	Management
Grade 2 colitis (abdominal pain, mucus or blood in stool)	
Pause RXC004 (and nivolumab if applicable)
 
Manage with corticosteroids at a dose of 0.5mg/kg methylprednisolone equivalent.
 
When symptoms have resolved, taper over 2-4 weeks.
 
If symptoms recur during tapering, the steroid dose may need to be increased again.
 
If no improvement in 72 hrs despite treatment, treat as Grade 3
 
RXC004 can be restarted at a lower dose after colitis has resolved to Grade <math>\leq 1^*</math> and steroids tapered to physiological levels (<10mg prednisone per day equivalent dose) over at least 1 month.
 
If steroids cannot be tapered to physiological levels within 12 weeks of commencing steroid treatment, then RXC004 (and nivolumab if applicable) should be permanently discontinued.

Grade 3 colitis ( severe or persistent abdominal pain, fever, ileus; peritoneal signs)	
Pause RXC004 (and nivolumab if applicable)
 
Seek specialist advice
 
Manage with corticosteroids at a dose of 1mg/kg methylprednisolone equivalent.
 
When symptoms improve, taper steroids to physiological levels over 4-8 weeks and consider use of prophylactic antibiotics and anti-fungals
 
If the patient is receiving RXC004 as a monotherapy, RXC004 can be restarted at a lower dose after colitis has resolved to Grade <math>\leq 1^*</math> and steroids tapered to

Grade	Management
	
physiological levels (<10mg prednisolone equivalent dose) over at least 1 month..
 
If the patient is receiving RXC004 in combination with nivolumab, both agents should be permanently discontinued
 
If steroids cannot be tapered to physiological levels within 12 weeks of commencing steroid treatment, then RXC004 (and nivolumab if applicable) should be permanently discontinued.
 
Additional anti-inflammatory medications (e.g infliximab) may be indicated if no improvement in 48-72 hrs. It is important to rule out bowel perforation and refer to infliximab SMPC/USPI for general guidance before using infliximab
 
If anti-inflammatories are required, RXC004 (and nivolumab if applicable) should be permanently discontinued.

Grade 4 colitis (life-threatening consequences)
	
Manage per Grade 3 Colitis.
 
RXC004 and nivolumab (if applicable) should be permanently discontinued.

\*Attempts should be made to confirm that the colitis has resolved to Grade  $\leq 1$  (e.g normalised CRP or fecal calprotectin if raised during event; GI appearance normalised on X ray/ CT or endoscopy) before restarting RXC004.

If there is any recurrence of colitis  $\geq$  Grade 2 after recommencing RXC004, **RXC004 and nivolumab (if applicable) should be permanently discontinued.**

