### **2.3.1.2 Allowed medication**

Patients will be permitted to receive appropriate supportive care measures as deemed necessary by the treating physician including but not limited to the items outlined below:

- Opiates may be used for pain control and patients can receive preventive treatment for constipation
- Hormone therapies are allowed for patients who have been identified as a hormone therapy user at the start of the study
- Anticoagulant Therapy: patients who are taking warfarin may participate in this trial; however, it is recommended that prothrombin time (international normalised ratio (INR) and activated partial thromboplastin time (APTT)) be monitored carefully at least once per week for the first month, then monthly if the INR is stable. Subcutaneous heparin is permitted.
- Diarrhoea: Diarrhoea should be promptly treated in line with the colitis management and treatment guidelines Appendix 5. Anti-diarrheal agents should not be taken prophylactically.
- Corticosteroids: Patients may receive on-study treatment oral or intravenous (i.v.) glucocorticoids for up to 4 weeks (at daily doses equivalent to  $\leq 10$  mg of oral (p.o.) prednisolone). If steroids are required for treatment of colitis (as per Appendix 5), then study treatment should be held until steroids are tapered to  $\leq 10$ mg per day prednisone or equivalent. . Patients enrolled on Module 2 (RXC004 and nivolumab) may also receive treatment with steroids for immune-mediated AEs (as per Appendix 8. Steroids should be tapered to  $\leq 10$  mg/day prednisone or equivalent before re-starting nivolumab. Patients who require treatment with  $\geq 10$ mg per day prednisone or equivalent for  $>8$  weeks should permanently discontinue study treatment (RXC004 and nivolumab if applicable).
- Patients may receive immunosuppressant (e.g. infliximab for colitis or mycophenolate for hepatitis) rescue medication required for colitis (as per Appendix 5) or nivolumab related immune mediated adverse events (as per Appendix 8). Steroid refractory patients that require immunosuppressant treatment should permanently discontinue study treatment (RXC004 and nivolumab if applicable).

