Grade < 3 toxicity (all events ^ )	Decision to interrupt RXC004 (max. 14 days*) is at the Investigator's discretion. Resume at same dose prior to interruption.
^ Excluding diarrhoea	
Surgery	Interrupt RXC004 (max. 14 days*), resume at full dose. RXC004 should be stopped 3 days prior to surgery and resumed approx. 10 days later. If the wound has not healed a further 7 days are permitted prior to re-starting RXC004 at the discretion of the Investigator and with approval of Sponsor Physician.  No stoppage is required for biopsy procedures.
Vomiting	If vomiting occurs shortly after RXC004 is swallowed, the dose may be replaced if all of the intact capsules can be counted. Resume with the following scheduled dose.
Missed dose	Allowed to take the scheduled dose up to 4 hours after the scheduled dose time. If greater than 4 hours, the missed dose should not be taken and patient should continue with next dose at allotted time.

Event	Action
Corticosteroid use	
Patients receiving corticosteroids for treatment of diarrhoea should hold RXC004 (for max. 14 days*) as per Diarrhoea/Colitis Management and Treatment Guidelines (please refer to Appendix 5)
 
Patients receiving corticosteroids for any indication other than diarrhoea, should continue RXC004 at current dose level.
 
Patients who require on-study oral or intravenous (i.v.) glucocorticoids for > 4weeks at daily doses equivalent to <math>\geq 7.5</math> mg of oral (p.o.) prednisolone (for any indication other than diarrhoea) should temporarily interrupt RXC004 (for a maximum of 14 days*) if receiving clinical benefit (in the opinion of the investigator) and resume at full RXC004 dose once the daily corticosteroid dose equivalent falls to <7.5 mg PO prednisolone.
 
RXC004 should be permanently discontinued for patients who require on-study oral or intravenous (i.v.) glucocorticoids for > 4weeks at daily doses equivalent to <math>\geq 7.5</math> mg of oral (p.o.) prednisolone and are not receiving clinical benefit from RXC004 (in the opinion of the investigator)

\* RXC004 interruptions of greater than 14 days may be allowed for patients judged by investigator to be clinically benefiting from study treatment, and only after consultation with Sponsor

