### 5.3.7 Dose Modifications

RXC004 dose reduction and interruption are permitted. Nivolumab dose reduction is not permitted but dose interruption/delay is permitted.

RXC004 may be dose interrupted (withheld) for up to 14 days until a clinically significant (any grade) and/or a grade  $\geq 3$  related adverse event resolves to baseline or  $\leq$  grade 1. Patients that experience a RXC004 related adverse events that do not resolve to baseline or  $\leq$  grade 1 after 14 days of dose interruption/delay despite appropriate treatment must be discussed with Sponsor, before re-starting RXC004.

Adverse events that are assessed as being causally related nivolumab should be managed as per the Nivolumab Toxicity Management and Dose Modification Guidelines (Appendix 8). If either agent alone is interrupted or discontinued for a related-AE the other agent (nivolumab or RXC004) may be continued if the patient is judged (by the investigator) to be receiving clinical benefit. If a patient continues in the study on nivolumab alone, this treatment may be continued for a maximum of 12 months in total.

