Event	Action
Any event that meets nivolumab treatment hold (see Appendix 8)	Interrupt nivolumab and manage as per Appendix 8. Nivolumab can be re-started when event is resolved to $\leq$ Grade 1 and any steroid taper completed (to 10mg prednisone equivalent). RXC004 can continue whilst nivolumab is held, if the patient is judged (by the investigator) to be receiving clinical benefit.
Grade 3-4 toxicity (1 st event)	RXC004 related;  Interrupt RXC004 and provide supportive care, resume at the next lowest dose level when resolved (grade $\leq$ 2 or returns to baseline). Interruptions >14 days should be discussed with Sponsor before re-starting.  Nivolumab related;  See guidelines in Appendix 8
Grade 3-4 toxicity (subsequent recurrence of a previously experienced event)	RXC004 and/or nivolumab related; Permanently discontinue study treatment
All Grade events	Study treatment can be discontinued for any clinically significant AEs that in the investigator's opinion warrants treatment discontinuation.

Event	Action
Bone events	
Confirmed RXC004 related fragility bone fracture (excluding grade 1 vertebral deformities)	Permanently discontinue RXC004. Nivolumab can continue, if clinical benefit is judged by investigator for a maximum of 12 months total treatment.
Patients with a DXA scan showing $\geq 7\%$ worsening in BMD at lumbar spine or total hip compared to baseline	Permanently discontinue RXC004. Nivolumab can continue, if clinical benefit is judged by investigator for a maximum of 12 months total treatment.
An individual increase in $\beta$ -CTX of $\geq 350$ pg/ml from the baseline (screening) value or in individual measurement of $\geq 1000$ pg/ml	Permanently discontinue study treatment unless the patient has received clinical benefit (investigator assessment) and continued treatment is warranted.
COVID-19 infection	
Positive COVID-19 test	Interrupt RXC004, until acute symptoms have resolved. Interruptions $>14$ days should be discussed with Sponsor before re-starting.
Surgery	Interrupt RXC004 (max. 14 days b ), resume at full dose. RXC004 should be stopped 3 days prior to surgery and resumed approx. 10 days later. If the wound has not healed a further 7 days are permitted prior to re-starting RXC004 at the discretion of the Investigator and with approval of Sponsor Physician.  No stoppage is required for biopsy procedures.

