	Thyrotoxicosis (DDx thyroiditis, Grave's disease)	
Investigations: Anti-TSH Receptor Ab, anti-TPO Ab, nuclear medicine thyroid uptake scan
 
Propranolol or atenolol for symptoms; consider carbimazole if anti-TSH Receptor Ab positive          Painful thyroiditis – consider prednisolone 0.5 mg/kg and taper if unwell,
 
Withhold dosea

Infusion reactions	Grade 1 or 2	Interrupt or slow rate of infusion
	Grade 3 or 4	Permanently discontinue
Other	Other Grade 3 AEs - First occurrence - Recurrence of same Grade 3 adverse events	
Withhold dosea
 
Permanently discontinue

	Life-threatening or Grade 4 adverse reaction	Permanently discontinue
	Grade 3 myocarditis	
If myocarditis is suspected, admit the patient and immediately start high-dose (methyl)prednisone (1–2mg/kg). In the case of deterioration, consider adding another immunosuppressive drug (MMF or tacrolimus)
 
Permanently discontinue

	Guillain-Barré syndrome (GBS)	
Nerve conduction studies (acute polyneuropathy)
 
Lumbar puncture (elevated protein with normal WBC count). Pulmonary function tests with vital

Adverse Event	Severity	Investigations, Treatment and Dose modification
		
capacity and maximum inspiratory/expiratory pressures. Antibody testing for GBS variants, e.g. GQ1b in Miller Fisher variant
 
Use of steroids not recommended in idiopathic GBS            If no improvement or worsening, plasmapheresis or intravenous immunoglobulin indicated.
 
Neurological consultation. Consider location of care where ventilatory support available (required in 15%-30% idiopathic cases)
 
Permanently discontinue

	Myasthenia Gravis	
Check for ocular muscle and proximal muscle fatigability. AChR and anti-MuSK antibodies
 
Bedside tests, e.g. Tensilon test or ice pack test with neurological input. Repetitive nerve stimulation and single fibre EMG
 
Steroids indicated (oral or i.v. depending on symptoms). Pyridostigmine initial dose 30 mg tds. If no improvement or worsening, plasmapheresis or IVIG may be considered
 
Additional immunosuppressants azathioprine, cyclosporine, mycophenolate
 
Avoid certain medications, e.g. ciprofloxacin, beta-blockers, that may precipitate cholinergic crisis
 
Neurological consultation
 
Permanently discontinue

	Requirement for 10mg per day or greater prednisone or equivalent for more than 12 weeks	Permanently discontinue

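### Two treatment rules conflict between protocol sections (the steroid-duration stop and the Module 2 restart grade), and Appendix 8 needs a cross-reference for Grade 3 colitis

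*Protocol*

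**What the plan says.** **Steroid duration.** The corticosteroid bullet in protocol Section 2.3.1.2 covers steroids given for colitis (Appendix 5) and, in Module 2, for immune-mediated events (Appendix 8). It ends with a stop for patients needing 10 mg/day or more of prednisone equivalent for more than 8 "weeks should permanently discontinue study treatment (RXC004 and nivolumab if applicable"). Appendix 5, which applies to all modules, stops treatment on a different condition, in both its Grade 2 and Grade 3 rows: "If steroids cannot be tapered to physiological levels within 12 weeks of commencing steroid treatment". Appendix 8 (Module 2 only) lists as a reason to stop "Requirement for 10mg per day or greater prednisone or equivalent for more than 12 weeks". Tables 6 and 7 give no week limit. Module 1 has its own steroid rule in Table 4 and is complete, so nothing is claimed for it.

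**Module 2 restart.** Section 5.3.7 allows RXC004 to be withheld for up to 14 days until a related Grade 3 or higher event is back to baseline or Grade 1 or lower. Events still unresolved "after 14 days of dose interruption/delay despite appropriate treatment must be discussed with Sponsor, before re-starting RXC004". Table 6, for a first RXC004-related Grade 3-4 event, says "resume at the next lowest dose level when resolved", and defines resolved as Grade 2 or lower, or baseline. Only interruptions longer than "14 days should be discussed with Sponsor before re-starting".

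**Grade 3 colitis on RXC004 plus nivolumab.** Table 6 and Appendix 5 both order a permanent stop of both drugs. The Grade 3 colitis row in Appendix 8 ends in an instruction to withhold the dose, marked with a footnote whose text is not in the file.

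**The concern.** These are safety instructions, and in two cases a site cannot follow all of them at once. A patient on steroids between weeks 8 and 12 must come off study treatment under one section and need not under two others. A Module 2 patient whose Grade 3 event has settled to Grade 2 within 14 days has not met the recovery threshold in one section and may be redosed under another. The protocol does not say which text prevails, so the page consulted can decide what happens.

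Colitis is a recognised RXC004 risk, and Appendix 5 warns that adding nivolumab may raise it. Reporting is touched as well: SAP Section IX.B tabulates events leading to withdrawal and to interruption separately, and a permanent stop for a related event makes a Module 3 patient evaluable under SAP Section VI.J, whereas a long hold may not.

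**Working it through.** There is no sample size, power or error rate to reproduce. The check compares the texts and counts days.

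**1. Steroid limit**

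- Section 2.3.1.2: 8 × 7 = 56 days. Appendices 5 and 8: 12 × 7 = 84 days.
- Disagreement: 84 − 56 = 28 days (day 57 to day 84). That is one 28-day Module 2 cycle, or 28/21 = 1.33 Module 3 cycles.

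Can a patient who follows the protocol reach day 57? Appendix 5's Grade 3 row says "When symptoms improve, taper steroids to physiological levels over 4-8 weeks", where physiological means below 10 mg. Assume the dose is at or above 10 mg from the start of steroids to the end of the taper. Then

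days at 10 mg or more = days before taper + 7 × taper weeks,

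and this passes 56 when the days before taper exceed 56 − 7 × taper weeks.

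| Taper | Days before taper needed to pass 56 | Total if symptoms improve at 2-3 days (assumed, from the row's 48-72 h point) |
|---|---|---|
| 4 weeks | more than 28 | 30-31 days |
| 6 weeks | more than 14 | 44-45 days |
| 8 weeks | more than 0 | 58-59 days |

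With improvement at 2-3 days, the taper must exceed (56 − 3)/7 = 7.57 to (56 − 2)/7 = 7.71 weeks to pass the 8-week limit. So only the longest permitted tapers do so, but an 8-week taper carried out as written does. Every total in the table is below 84 days.

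What the conflict changes depends on the event:

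- *Colitis.* RXC004 is held until steroids are tapered (Section 2.3.1.2, Tables 6 and 7, Appendix 5). Between days 57 and 84 nobody should be taking it under any of these texts. The limit decides whether a patient who finishes the taper in that window may restart.
- *Other nivolumab immune events.* Table 6 lets RXC004 continue during a nivolumab hold if the investigator sees benefit. Grade 2 pneumonitis in Appendix 8 is such a hold, with weaning over at least 6 weeks once back to baseline. If the dose stayed at 10 mg or more throughout (an assumption, as the row gives no end dose), a 6-week wean passes 56 days when recovery to baseline took more than 56 − 42 = 14 days. Here the conflict bears on RXC004 dosing itself.

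**2. Module 2 restart after a related Grade 3 or higher event (not colitis)**

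| State of the event | Section 5.3.7 | Table 6, first Grade 3-4 event |
|---|---|---|
| Grade 1 or lower, or baseline | Resolved | Resume one dose level down |
| Grade 2, baseline lower, within 14 days | Not yet resolved | Resume one dose level down, no Sponsor contact |
| Grade 2, baseline lower, beyond 14 days | Discuss with Sponsor | Discuss with Sponsor |

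The texts part only in the middle row, a window of 14 days (14/28 = half a cycle). Module 3 also restarts at Grade 2 or lower, but Section 5.4.6 requires the Sponsor physician's agreement.

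**3. Grade 3 colitis on the combination**

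Two texts order the stop. Appendix 8's row says to withhold and does not confine itself to patients left on nivolumab alone, for whom a hold can be proper. What is missing is a pointer to Table 6.

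**The case against.** Several counter-arguments are sound and limit the point.

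- A reader might infer that colitis patients keep taking RXC004 through weeks 8 to 12 of steroids. They do not, because the drug is held. In Module 3, restart also needs the Sponsor physician's agreement. The 8-versus-12-week conflict remains, as a question of who may restart.
- Long periods before the taper fit poorly with Appendix 5. If there is no improvement in 48-72 h, further anti-inflammatory treatment may be indicated, and needing it ends study treatment. Crossing day 56 by the Grade 3 route therefore takes a taper near the 8-week maximum. Other routes exist: the Grade 2 row foresees raising steroids again if symptoms return.
- It is tempting to adopt 8 weeks as the stricter value. On its own, that would remove patients who followed the Grade 3 taper exactly. Twelve weeks appears in two of the three texts and fits the tapers.
- Section 5.3.7 is permissive about interrupting, and is mandatory only on Sponsor discussion after 14 days. Table 6 restarts at a reduced dose, and Grade 2 or lower matches Modules 1 and 3. All true, but the two recovery thresholds still differ for the same event.
- A reader might count Grade 3 colitis as a third conflict, or infer that the plan allows redosing on the combination. The documents do not support this: the stop is explicit in Table 6 and Appendix 5, and Appendix 8's footnote cannot be read.
- A reader might also see contradictory entry criteria in Section 3.4.1.1, whose glucocorticoid look-back is 12 weeks against 6 in Section 2.2.1. Section 2.2.1 is the eligibility list, so this is editorial.
- SAP Table 2 shows Module 2 actual doses of 1 and 1.5 mg only, and SAP Table 3 lists one Module 3 schedule, so few patients may be left to benefit. The documents do not say dosing has ended.

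**Conclusion.** The point holds for two rules, and as a drafting gap for a third. The steroid limits differ by 28 days in Modules 2 and 3. The difference governs restart after colitis, and possibly RXC004 dosing in other nivolumab immune events. The Module 2 restart thresholds differ by one grade for interruptions of up to 14 days, where Table 6 asks for no Sponsor contact. The Sponsor checks after 14 days and in Section 5.4.6 reduce the risk but do not remove it: none sets a steroid limit, and none covers an early Module 2 restart under Table 6. Grade 3 colitis on the combination is already a permanent stop and needs only a pointer.

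The conflicts rest on the text alone. The taper totals rest on the assumed 2-3 days to improvement and on the dose staying at 10 mg or more until the taper ends. The number of patients affected cannot be derived from the documents. It should be fixed as a safety matter; it bears on no sample size or error rate.

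**What to change.** 1. **Steroid limit, Modules 2 and 3.** State one limit in Section 2.3.1.2 and Appendices 5 and 8. Twelve weeks fits the existing tapers. If the sponsor keeps 8 weeks, shorten Appendix 5's Grade 3 taper or say in that row that patients past the limit do not restart. Leave Table 4's Module 1 rule alone.
2. **Restart grade, Module 2.** Use one grade in Section 5.3.7 and in Table 6's first Grade 3-4 row. Baseline or Grade 1 or lower is the conservative choice for the combination. If Grade 2 or lower is kept, require Sponsor agreement as Section 5.4.6 does for Module 3.
3. **Appendix 8, Grade 3 colitis row.** Add that patients on RXC004 plus nivolumab stop both drugs permanently, per Table 6.
4. **Editorial.** Replace the list in Section 3.4.1.1 with a reference to Section 2.2.1.

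The cost is one protocol amendment, with no added patients, visits or procedures. It is more than editorial because it settles treatment rules. The stricter restart grade means some longer holds, and an 8-week limit would end treatment for some patients who could restart under 12.
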